10.7.2 Primary Analysis

All analyses will be based on data from the 144 evaluable women (women with at least one follow-up visit in each period of the study) after assessing differences in baseline values between the evaluable women and those women lost to follow-up. These differences will be described and used to interpret the generalizability of the results. For the adherence endpoint, the primary analysis will evaluate the difference in product adherence using statistical methods for paired data controlling for period and sequence effects. Prior to this analysis, the presence of any carryover effects will be evaluated using a more liberal alpha level of 10%. Although carryover effects are not expected, if evidence of them is found, we will resort to analyzing only the data from the first period as a simple three arm parallel design using statistical methods for independent data. This will greatly reduce the power of testing. If adherence distributions do not allow the use of parametric tests, rank tests as those described in Koch and Strokes will be used instead.¹³

For the binary acceptability endpoint, similar measures to assess for carryover effects will be used and then for the main outcome, controlling for period and sequence effects, a generalization of McCullagh's proportional odds model for repeated measures will be performed by adding a random effect on the logit scale as proposed by Ezzet and Whitehead.¹⁴ Again, if carryover effects are present, the analysis will only use data from the first period.

Blood and intracellular samples will be analyzed for routine PK parameters - C_{max} , T_{max} , AUC, C_{min} - and described using descriptive statistics. Cervical and vaginal samples will be analyzed using sparse sampling population PK methods to provide PK parameter estimates. Measures of drug exposure (AUC, C_{max}) will be compared between oral and vaginal and dual use concentration differences controlling for sequence and period effects. Post-biopsy blood samples will be evaluated for deviation from expected values. Model building will be attempted to relate blood and intracellular model drug levels if sufficient samples have detectable drug levels.

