4.5 Study Groups

Six study sequences are planned. The 144 planned participants will be randomized equally across all 6 sequences in a 1:1:1:1:1 ratio. All study participants will be assigned to complete each study period (oral, gel, oral plus gel) once in an order that will be randomly assigned. Up to 204 women may be enrolled to reach the target of 144 evaluable women (i.e., women who have at least one follow-up visit with adherence data in each of the three periods of the study). The need to enroll replacement participants for enrollees will be dependent on whether the enrollee had at least one full period of the study with no follow-up adherence data. Details on procedures for

participant replacement are outlined in the MTN-001 Study Specific Procedures (SSP) Manual (www.mtnstopshiv.org).

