However, a participant who has been permanently discontinued from either type of study product will not take any study product during the Dual Formulation Period (if this study period has not yet begun for an individual participant), but will be followed according to regularly scheduled evaluations of safety, according to Section 7.4.5.

Participants may initiate study product use per protocol in a subsequent study period (if applicable), provided other product hold guidelines do not apply. Participants must meet applicable criteria for restarting a particular study product before initiating that study product's use in a subsequent study period.

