10.2.2 Study Secondary Endpoints

Consistent with the secondary study objectives, the following secondary endpoints will be assessed:

- Proportion of women who report taking at least 90% of expected daily doses, frequency of use during the follow-up interval using an ordinal measure (5 categories of use, never to always); number of days product missed or not used during the previous week
- Frequency (ordinal measures) of sexual activity and male condom use
- Time interval between product usage and sexual intercourse; sequence of product use and sexual intercourse
- Reported sharing of study product; quantity of shared study product
- Grade 3 or higher toxicity for systemic and local effects as defined by DAIDS AE Grading Table Version 1.0, December 2004, or Grade 3 or higher genital infection, pain or epithelial lesion as defined by the Female Genital Grading Table for Use in Microbicide Studies which cannot be directly attributed to another cause, and judged as definitely, probably, possibly, or probably not related to the study gel, applicator, or study tablet

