10.6 Participant Accrual, Follow-up, Retention, and Replacement

The accrual period will be 6 months. Up to 204 women may be enrolled to reach the target of 144 evaluable women, where evaluable women are women who have at least one follow-up visit with adherence data in each of the 3 periods of the study. Five of the 7 participating sites will recruit and enroll 24 evaluable participants each, and 2 of the participants sites will enroll 12 evaluable participants each for a total of 144 evaluable participants. The need to enroll replacement participants for enrollees will be dependent on whether the enrollee had at least one full period of the study with no follow-up adherence data. Details on procedures for participant replacement are outlined in the SSP Manual.

Each participant will be followed for 21 consecutive weeks (three periods of 7 weeks). In a crossover study, it is important to have completeness of the data such that the target retention should be set at 100%. Therefore, once a participant has enrolled in the study, the study site will make every reasonable effort to retain her for the entire study period so that she is evaluable. A maximum of 5% loss-to-follow-up of enrolled participants is targeted.

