13.6.1 Pregnant Women

Participants who test positive for pregnancy at screening or enrollment visits will not be eligible to participate in this study. A urine pregnancy test will be performed on all women at all clinic visits, and participants who test positive will be taken off product. During the informed consent process, women will be informed that oral tenofovir disoproxil fumarate and tenofovir gel are not methods of contraception and that the effects of oral tenofovir disoproxil fumarate and tenofovir gel on a developing human fetus are unknown.

Oral TDF is classified by the FDA as a Pregnancy Category B drug. Animal studies have failed to demonstrate a risk to the fetus, but there are no adequate and well-controlled studies in pregnant women that have been completed to date.

All potential participants will be required by the Eligibility Criteria for Screening and Enrollment to be currently using a reliable method of contraception, such as hormonal contraception (except vaginal ring), intrauterine device, or sterilization. Women who become pregnant during the study period following randomization and exposure to study product will discontinue product use and the PK assessments but will not be excluded from analysis.

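### All analyses are restricted to women with data in all three periods, a status fixed after randomisation, defined in two ways, and with no separate set for safety or the Period 1 fallback

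*Protocol*

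**What the plan says.** Section 10.7.2 fixes the analysis set: "All analyses will be based on data from the 144 evaluable women". In the same sentence it describes these as "women with at least one follow-up visit in each period of the study". Section 4.5 describes them differently, as "women who have at least one follow-up visit with adherence data in each of the three periods of the study", and Section 10.6 repeats that version: "evaluable women are women who have at least one follow-up visit with adherence data in each of the 3 periods of the study". Under 4.5 and 10.6, replacement turns on "whether the enrollee had at least one full period of the study with no follow-up adherence data", with up to 204 women enrolled to reach 144 evaluable. Section 10.6 targets loss to follow-up of no more than 5%.

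For women outside the set, 10.7.2 provides a comparison of baseline values between evaluable women and those lost to follow-up, to be described and used when judging generalizability. Nothing else is planned for them.

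Three other places bear on the point:
- Section 10.2.2 lists "Grade 3 or higher toxicity for systemic and local effects" among the secondary endpoints. No separate safety population is stated.
- Section 9.4 says that "a participant who has been permanently discontinued from either type of study product will not take any study product during the Dual Formulation Period", if that period has not yet begun for her.
- Section 13.6.1 says that women who become pregnant after randomisation and exposure "will discontinue product use and the PK assessments but will not be excluded from analysis".

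**The concern.** Whether a woman is evaluable depends on what happens to her after randomisation. Leaving because a regimen is disliked or poorly tolerated lies close to the primary endpoints themselves, self-reported adherence and being unlikely to use the product in future. Under the rule, such a woman loses her place in the comparison of every regimen, including those she used and reported on, and another woman is enrolled instead.

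Two analyses suffer in particular. First, safety: a woman who uses a product in Period 1, has a Grade 3 event and leaves is, on the literal wording, in neither numerator nor denominator. Second, the carryover fallback in 10.7.2, which treats Period 1 as a three-arm parallel comparison. Data in Periods 2 and 3 have no bearing on that comparison. Requiring them selects women differently according to their first regimen if exit depends on that regimen, and the arms compared are then no longer the randomised groups.

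Section 2.1 says the results will inform the design of a later Phase 2B trial, so it matters which women the estimates describe.

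**Working it through.** **1. The plan's own power figure.** Inputs from 10.4: SD 20 points, rho 0.5, 144 evaluable women, two-sided alpha 5%, N' = N(1 − rho)/2. The equivalent parallel size is 144/(1 − 0.5) = 288 per arm. The standard error is 20 × √(2/288) = 1.667, so power for 5 points is Φ(5/1.667 − 1.96) = Φ(1.04) = 85.1%, against 85% in Table 13. The other cells of Table 13 also reproduce. The power arithmetic is not at issue; 5 points serves below only as a yardstick.

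**2. Share of enrolled women outside every analysis.**
- At the cap: (204 − 144)/204 = 60/204 = 29.4%.
- At the loss target: 144/0.95 ≈ 152 enrolled, and 8/152 = 5.3%. This assumes that loss is the only route to being non-evaluable and that every lost woman misses a whole period. A woman lost late in Period 3 may still be evaluable.

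**3. What it would take to matter for adherence.** Shift in the regimen difference = excluded share × gap, where the gap is the regimen difference in excluded women minus that in evaluable women. The documents give no value for the gap.
- Gap needed for a 5-point shift: 5/0.294 = 17 points at the cap; 5/0.0526 = 95 points at the loss target.
- For assumed gaps of 10, 20 and 30 points: 2.9, 5.9 and 8.8 points at the cap; 0.5, 1.1 and 1.6 points at the target.

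**4. Acceptability, illustration with assumed rates.** Suppose 5% of evaluable women and 20% to 50% of excluded women would be unlikely to use a product. At the cap, the rate in all enrolled women is 0.706 × 5 + 0.294 × 20 = 9.4%, up to 0.706 × 5 + 0.294 × 50 = 18.2%. At the target it is 5.8% to 7.4%. The evaluable-only analysis reports 5% in each case.

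**5. Period 1 fallback.** Each regimen opens two sequences, so 144 evaluable women give 48 per arm. If all 204 women were enrolled, balanced, and gave Period 1 data, there would be 68 per arm. Power = Φ(d/(20√(2/n)) − 1.96):
- 5 points: 23% with 48 per arm, 31% with 68.
- 7.5 points: 45% and 59%.
- 10 points: 69% and 83%.

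The protocol itself notes that the fallback greatly reduces power; the restriction can reduce it further. At 152 enrolled there is little to recover.

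**6. Safety precision.** With zero Grade 3 or higher events, the one-sided 95% upper bound is 1 − 0.05^(1/n): 2.1% for n = 144 and 1.5% for n = 204.

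**7. The two definitions applied to women off product.** Sections 7.4.2, 7.4.4 and 7.4.5 continue all procedures except product supply, product-use counselling (for voluntary or investigator discontinuation, only if both products are stopped) and PK. Behavioural assessments are not among the exceptions, and Appendix I schedules two per period.
- Visit-based wording (10.7.2): a woman off product who attends in each period is evaluable.
- Adherence-data wording (4.5, 10.6): she is evaluable only if adherence data are recorded in a period when she is given no product, such as the dual period under 9.4. The protocol does not say whether they are.
- Pregnant women: 13.6.1 agrees with 10.7.2 for those who attend in each period. It conflicts if they leave, or under the other definition if no adherence data are recorded.

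**The case against.** **The restriction may not reach safety.** The sentence stands under a heading about the primary analysis, and that section describes methods only for adherence, acceptability and PK. A safety set is commonly left to the SAP, which is not at hand. This has force, but the wording covers all analyses without exception, and a SAP with another safety set would have to depart from it. A reader might also infer that severe events in early leavers are lost to the trial. They are not: Section 8.3.1 records adverse events from random assignment, and 8.1 and 8.2 provide for ongoing safety review. What is at risk is their place in the regimen comparison.

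**Women who stop product need not drop out.** A reader of 9.4 might infer that a permanent stop almost certainly makes a woman non-evaluable. The documents do not support this. She is encouraged to remain, nearly all procedures continue, she may still enter the other single-product period, and in Sequences C and D the dual period comes first. Likewise, 13.6.1 does not flatly contradict 10.7.2. This objection stands; the problem is confined to women who leave and to the unresolved definition.

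**The share excluded may be small.** The figure of 204 is a ceiling, and the stated target is 5% loss. This also stands.

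**Pairing is a reason for complete cases.** Among completers, each regimen comparison is within woman. That supports a complete-case analysis as one analysis, but not for safety or the Period 1 fallback. The baseline comparison is a real safeguard, but a descriptive one: it adjusts nothing, and it names only women lost to follow-up, not those who attend but lack adherence data for a period.

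**Conclusion.** The point holds. The protocol fixes a post-randomisation subset for all analyses, replaces the women outside it, and states no other set for Grade 3 or higher toxicity or for the Period 1 fallback. It also gives two definitions of evaluable that can classify the same woman differently. These are faults of the text and need no estimate of bias.

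The size is uncertain. The excluded share is about 5% if loss meets its target and at most 29% if 144 evaluable women are reached at the cap. At 5%, bias in the adherence comparison is likely small. At 29%, a gap of 17 points between excluded and evaluable women would shift the difference by 5 points, but that gap is an assumption. A reader might infer that the restriction pulls the results towards the hypothesised absence of difference. The documents do not show this: the direction depends on which regimen drives women out. The case for change rests most firmly on the safety set, the fallback and the definitions.

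**What to change.** - Keep 144 evaluable women as the enrolment and replacement target only.
- Analyse adherence and acceptability in all randomised women with at least one record on a regimen, using a mixed model with a random effect for woman and terms for regimen, period and sequence. The acceptability analysis in 10.7.2 already uses a random-effects model.
- If the carryover fallback is triggered, use all women with Period 1 data.
- Report safety in all women who used at least one dose, assigning events to the regimen in use plus its washout week. Section 10.1 already uses that week to collect events from the preceding period.
- Keep the 144-evaluable analysis as a sensitivity analysis.
- Use one definition of evaluable in 4.5, 10.6 and 10.7.2, say whether adherence data are recorded in periods without product, and align 13.6.1 with it.

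The cost is a paragraph in 10.7.2, small edits elsewhere and matching SAP wording. No new data collection or sample size is needed. The limitation is that the mixed model treats absent periods as missing at random. It recovers the periods now discarded but may not fully correct for dropout caused by a regimen, so reasons for leaving should be reported by the regimen in use at the time.

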11 DATA HANDLING AND RECORDKEEPING

11.1 Data Management Responsibilities

Study case report forms will be developed by the SDMC. Quality control reports and queries routinely will be generated and distributed by the SDMC to the study sites for verification and resolution.

11.2 Source Documents and Access to Source Data/Documents

Source documents and access to source data/documents will be maintained in accordance with the Requirements for Source Documentation in DAIDS Funded and/or Sponsored Clinical Trials. The investigator will maintain, and store securely, complete, accurate and current study records throughout the study. In accordance with US regulations, the investigator will retain all study records on site for at least two years after study closure. Study records will not be destroyed prior to receiving approval for record destruction from DAIDS. Applicable records include source documents, site registration documents and reports, correspondence, informed consent forms, and notations of all contacts with the participant.

11.3 Quality Control and Quality Assurance

Quality control and quality assurance procedures for MTN-001 will be performed in accordance with Requirements for Clinical Quality Management Plans at DAIDS Funded and/or Supported Clinical Research Sites.

11.4 Study Coordination

DAIDS holds the IND applications for this study. Assignment of all sponsor responsibilities for this study will be specified in a Clinical Trials Agreement executed by DAIDS, CONRAD, and Gilead Sciences, Inc. Study site staff will be provided with the DAIDS SOPs for Source Documentation and Essential Documents, the Manual for Expedited Reporting of Adverse Events to DAIDS, and the DAIDS AE Grading Table. Training and written instructions outlining management and reporting, study gel dispensing, product accountability, and other study operations will be provided by FHI, SCHARP, and the MTN NL.

12 CLINICAL SITE MONITORING

Study monitoring will be carried out by PPD (Wilmington, NC). On-site study monitoring will be performed in accordance with Requirements for On-Site Monitoring of DAIDS Funded and/or Sponsored Clinical Trials. Site monitoring visits will be conducted to assess compliance with Health and Human Services (HHS) Regulations 45 Code of

Federal Regulations (CFR) Part 46 and 21 CFR Parts 50, 56, and 312. Study monitors will visit the site to:

- Verify compliance with human subjects and other research regulations and guidelines, including confidentiality procedures, informed consent process, and regulatory documentation
- Assess adherence to the study protocol, SSP Manual, and local counseling practices
- Confirm the quality and accuracy of information collected at the study site and entered into the study database, including the validation of data reported on case report and DataFax forms
- Assess the resolution of any past or ongoing issues identified at previous monitoring visits

Site investigators will allow study monitors to inspect study facilities and documentation (e.g., informed consent forms, clinic and laboratory records, other source documents, case report forms), as well as observe the performance of study procedures. Investigators also will allow inspection of all study-related documentation by authorized representatives of the MTN CORE, MTN NL, FHI, SCHARP, NIAID, local regulatory authorities, and US regulatory authorities. A site visit log will be maintained at the study site to document all visits.

13 HUMAN SUBJECTS PROTECTIONS

The investigators will make efforts to minimize risks to human participants. Volunteers and study staff members will take part in a thorough informed consent process. Before beginning the study, the investigators will have obtained IRB/EC approval and the protocol will have been submitted to the FDA. The investigators will permit audits by the NIH, CONRAD, Gilead Sciences, Inc., the FDA, or any of their appointed agents.

13.1 Institutional Review Boards

Each participating institution is responsible for assuring that this protocol and the associated informed consent documents and study-related documents are reviewed by an EC or IRB prior to implementation of the protocol. Any amendments to the protocol, informed consents, or other study- related documents must be approved by the IRB/EC and DAIDS prior to implementation.

13.2 Protocol Registration

Each study site will complete protocol registration with the DAIDS RCC Protocol Registration Office. Protocol registration material can be sent electronically to

[contact]. For questions regarding protocol registration, please call [contact]. For additional information, refer to the protocol registration documents located at http://rcc.tech-res.com/forms.htm.

Protocol registration must occur as a condition for site-specific study activation; no participants may be screened or enrolled in this study prior to obtaining protocol registration approval and completing all other study activation requirements. MTN CORE (FHI) staff will notify each study site when all activation requirements have been met by issuing a site-specific study activation notice. Study implementation may not be initiated until the activation notice is issued.

The study will be conducted in full compliance with the protocol. The protocol will not be amended without prior written approval by the Protocol Chair and DAIDS Medical Officer. All protocol amendments must be submitted to and approved by the relevant IRB/EC(s) and the RCC prior to implementing the amendment.

13.3 Risk Benefit Statement

13.3.1 Risks

Phlebotomy may lead to discomfort, feelings of dizziness or faintness, and/or bruising, swelling and/or infection. Pelvic examination may cause mild discomfort and/or vaginal bleeding or spotting. Disclosure of STI status may cause sadness or depression in volunteers. Participation in clinical research includes the risks of loss of confidentiality and discomfort with personal nature of questions.

For sub-study participants, vaginal biopsy carries the risk of discomfort or pain during the procedure and for a few hours afterwards. Participants may have mild vaginal spotting (bleeding) for one or two days, and will be instructed to avoid sexual intercourse until bleeding stops. Some temporary discomfort with sexual intercourse may occur if the biopsy areas are still healing. There is a small risk of infection and heavier bleeding. Participants will be instructed to contact the clinic if symptoms are bothersome, if heavy bleeding is noted (soaking through a pad or tampon in an hour or less) or if the participant develops any abnormal odor or discharge from the vagina.

The most common side effects associated with oral TDF in patients with HIV infection are nausea, headache, diarrhea, vomiting, asthenia, flatulence, abdominal distension/pain and anorexia. Less common side effects of TDF include kidney toxicities and low blood phosphate. Other side effects reported in the post-marketing period include weakness, pancreatitis, low blood phosphate, dizziness, shortness of breath, and rash. In animal studies, tenofovir has been associated with decreased bone mineral density. These effects have not been seen in those taking tenofovir tablets for up to one year.

Redistribution/accumulation of body fat including central obesity, dorsocervical fat enlargement (buffalo hump), peripheral wasting, facial wasting, breast enlargement, and

"cushingoid appearance" have been observed in persons receiving antiretroviral drugs. The mechanism and long-term consequences of these events are currently unknown. A causal relationship has not been established. These effects are not expected in this study involving a brief exposure to antiretroviral drug.

Administration of tenofovir gel intravaginally at 0.3% and 1% concentrations in the HPTN 050 Phase1 study resulted in minimal local irritation and little or no systemic adverse effects were identified.⁸ Although 92% of participants reported at least 1 AE, 87% of those reported AEs were mild, and 70% of the AEs were limited to the genitourinary tract. Four severe AEs were reported, with only one, lower abdominal pain, thought to be product-related. The risks associated with tenofovir gel are believed to be less than those identified for systemic use. In the HPTN 050 Phase1 study of tenofovir gel, serum PK analysis in a subset of participants demonstrated that there is no clinically significant systemic toxicity. Fourteen of 25 women with PK results had low, but detectable, serum tenofovir levels.

Given that Phase 1 data demonstrates measurable plasma concentrations of tenofovir in some participants, participants with hepatitis B infection might be at risk for development of tenofovir resistant hepatitis B. However, participants with known hepatitis B infection will not be eligible for enrollment. It is not known what effect tenofovir gel could have on the HIV virus or HIV disease progression in HIV infected participants or their partners. There is a theoretical risk that tenofovir absorbed systemically from tenofovir gel could result in mutations of the HIV virus in participants who become infected with HIV during the study, or their partner, if the partner is infected with HIV. Limited resistance data from HPTN 050 show no new resistance mutations in plasma or CVL specimens after 14 days of tenofovir gel use. No participant had high level tenofovir mutations (e.g. K65R). Some of the possible side effects of the study gel are dryness, itching, burning, or pain in the genital area.

